5.1.3 Postoperative Visits – Day 1 to Day 1170

Each treated eye will be seen for 8 postoperative visits according to the schedule in Appendix A. Postoperative visits for both eyes may be scheduled on the same day only if the study visit window for each eye allows.

5.1.4 Unscheduled Visits

Additional visits may be scheduled, as necessary, to ensure the safety and well-being of subjects. All additional exams should be fully documented in the source documents and on Unscheduled Visit case report forms (CRFs), as appropriate. Visits intended to fulfill scheduled visit requirements that fall outside the designated scheduled visit range, will also be captured on Unscheduled Visit CRFs. In these cases, the intended visit will be identified on the Unscheduled Visit CRF.

5.1.5 Missed Visits

Site personnel will make every effort to avoid missing data, for example, by scheduling visits early in each visit window, calling subjects to remind them of upcoming visits and promptly calling subjects who have missed a visit in order to reschedule their visit within the appropriate window. If, despite best efforts, a missed visit cannot be rescheduled, the visit will be documented as missed in the source documents and CRFs.

5.2 Study Completion

STAAR Surgical will notify the Investigator when to contact the IRB to inform them that the study is complete.

5.2.1 Early Study Termination

If during the study it becomes evident to the Sponsor that the study should be stopped prematurely, the study will be terminated and appropriate notification will be given to the Investigator(s), IRB, and FDA, as applicable. STAAR Surgical will instruct the Investigators to stop dispensing study materials/treatment, to assure appropriate follow-up for all enrolled subjects and arrange for study closeout at each site as appropriate.

In addition, should the study be discontinued prior to bilateral implantation, STAAR surgical will provide an appropriate commercially available ICL or suitable alternative refractive procedure for the subject's fellow eye.

5.2.2 Post-study Follow-up

If a subject requires further follow-up of SAEs upon discontinuation or completion of the study, the Investigator should schedule post-study follow-up visits, as necessary. Refer to Section 6.3.4 for follow-up of SAEs following study exit.

5.3 Concomitant Medications/Therapy

5.3.1 Perioperative Medication Regimen

The following medication regimen will be followed by all sites:

- topical 4th generation fluoroquinolone QID starting 3 days prior to surgery for a total of 10 days,
- topical NSAID QID, BID or QD per NSAID labeled dosing instructions for postoperative inflammation starting 3 days prior to surgery for a total of 10 days and then tapered weekly through 28 days after surgery,
- topical steroid QID starting 3 days prior to surgery for a total of 10 days and then tapered weekly through 28 days after surgery.

Note: No prophylactic systemic or topical IOP lowering medications (e.g., acetazolamide) will be used.

During the study follow-up period, the Investigator may use any medical treatment that is judged appropriate and beneficial to the subject. All medications that are considered necessary for the subject's welfare may be used at the Investigator's discretion. Documentation of all medications used for ocular indications by the subject during this study will be recorded in the subject's source document and applicable CRFs.

5.4 Protocol Deviations

The date of and reason for deviations will be documented in all cases. Significant or major protocol deviations impacting the safety of the subject or the integrity of the study must be reported by the Investigator to the Sponsor and IRB immediately. Reporting of all other protocol deviations must adhere to the requirements of the governing IRB.

Protocol assessments will continue until the end of the study, unless the protocol deviations put the subject at risk or the subject's condition requires that he/she be discontinued from the study.

6.0 ADVERSE EVENT REPORTING

Throughout the course of this study, all efforts will be made to remain alert to possible AEs. If an AE occurs, the first concern will be the safety of the subject, and appropriate medical intervention will be made. All ocular AEs (only eyes implanted with study lenses) and all serious AEs (both ocular and non-ocular) will be reported in this study. Non-serious non-ocular AEs will not be reported. The collection of AEs begins at the time the subject completes the informed consent process to participate in the study.

Refer to Section 6.3.1 for instructions on events that require expedited reporting to the Sponsor.

6.1 Definitions

6.1.1 Adverse Event

An **Adverse Event (AE)** is any untoward medical occurrence in a subject that does not necessarily have a causal relationship to the study device and study protocol. Adverse events include **Adverse Device Effects (ADEs)**.

In this study, all untoward events (aside from the exceptions noted for the early postoperative period in the following sections) that occur during the study need to be reported as AEs. In addition, all secondary surgical interventions (SSIs) and events that cause these interventions, and all events that have sequelae should be reported as AEs, regardless of when they occur.

AEs Associated with IOLs

Complications during phakic IOL surgery must be reported as AEs on the AE CRF. A worsening of a pre-existing ocular condition during the study should be documented as an AE and evaluated according to the guidelines in Section 6.2. All events that have sequelae should be reported as AEs, regardless of when they occur.

Adverse events associated with implantation of all types of IOLs (i.e., aphakic and phakic), need to be reported in this study. These can include, but are not limited to the following:

- **Chronic Anterior Uveitis:** anterior segment inflammation characterized by grade 1+ cell or greater that is persistent for > 3 months after surgery, or relapses in < 3 months after discontinuation of therapy, or for which the subject is maintained on therapy for > 3 months to control inflammation should be reported as an AE. In addition, anterior chamber (AC) cells or flare of greater than grade 2 (using the Standardization of Uveitis Nomenclature, SUN criteria¹⁰) at Visit 2 (Day 5 – 9) or later should be reported as an AE.
- **Clinically significant cystoid macular edema (CME):** macular edema diagnosed by clinical examination and adjunct testing (e.g., optical coherence topography [OCT], fluorescein angiography) resulting in CDVA of 20/40 or worse at Visit 3 (Day 21 – 35) or later.
- **Clinically significant corneal edema:** corneal swelling (stromal or epithelial) at Visit 2 (Day 5 – 9) or later should be reported as an AE.
- **Endophthalmitis:** intraocular inflammation requiring diagnostic vitreous tap and intraocular antibiotics,
- **Mechanical pupillary block:** shallowing of anterior chamber due to obstruction of aqueous humor flow from the posterior to anterior chamber through the pupil by the crystalline lens, vitreous face, or implanted device.
- **Rhegmatogenous retinal detachment (RD):** partial or complete RD associated with retinal tear.

- Toxic anterior segment syndrome (TASS): acute, non-infectious inflammation of the anterior segment that starts within 24 to 48 hours after surgery, usually resulting in hypopyon and commonly presenting with corneal edema and improving with steroid treatment.
 - All SSIs and events that cause these interventions should be reported as AEs, regardless of when they occur.
 - For SSIs of secondary IOL intervention*
 - Exchange – investigational device is replaced with the same lens model
 - Removal – investigational device is removed and replaced with a non-investigational lens or no lens is implanted
 - Reposition – existing IOL is surgically moved to another location or rotated
- *Exchanges, removals, and repositions should be further sub-categorized by the problem that caused the need for the intervention (e.g., pupil ovalization, subject-reported undesirable optical phenomena, damaged IOL, malpositioned IOL, lens optic abnormality, iris pigment epithelial loss, endothelial cell loss, incorrect IOL power, chronic anterior uveitis, cataract, etc.).

Experience with intraocular surgery and the implantation of IOLs has shown that some events can be considered normal or expected after these procedures. Early, low grade anterior chamber cell/flare, corneal edema, and increase in IOP can often be considered normal or expected after phakic IOL surgery. They do not need to be reported as AEs if they occur prior to 1 week postoperatively and if they meet the following criteria:

- AC cells or flare of grade 2 (using the Standardization of Uveitis Nomenclature, SUN criteria)¹⁰ or less that require no change in standard postoperative medication regimen; if persisting to 1 week or more these **should** be reported as an AE.
- Corneal edema of \leq grade 2 that does not reduce CDVA to 20/40 or worse and does not require any change in standard postoperative medication regimen; if corneal edema persists to 1 week or more it **should** be reported as an AE.
- Increased IOP that is <10 mmHg above baseline or is <25 mmHg and requires no change in standard postoperative medication regimen or any other special treatment; increased IOP ≥ 10 mmHg above baseline to a minimum of 25 mmHg at one week or later **should** be reported as an AE.
- Loss of CDVA ≥ 10 letters up to 1 week postoperatively; loss of CDVA ≥ 10 letters at any time point > 1 week postoperatively **should** be reported as an AE.
- All other untoward events that occur during the study, and all events that have sequelae **should** be reported as AEs, regardless of when they occur.

AEs Associated with the ICL Platform

Ocular AEs associated with the ICL platform will be reported in this study. These can include, but are not limited to the following:

- anterior subcapsular opacities or clinically significant anterior subcapsular cataracts
- narrowing of the anterior chamber angle
- glaucoma
- corneal endothelial cell loss
- loss of CDVA
- increase in refractive astigmatism
- pigment dispersion
- iris transillumination defects

In addition, ocular AEs associated with the ICL platform may require a secondary surgery in the implanted eye(s). The following surgeries have been associated with the ICL platform:

- secondary IOL intervention (see above*)
- vitreous aspiration
- iridotomy/iridectomy for pupillary block
- wound leak repair
- retinal detachment repair
- corneal transplantation

All ocular AEs that fall outside of the above definitions should still be reported as AEs. In addition all SSIs and events that cause these interventions, and, all events that have sequelae should be reported as AEs, regardless of when they occur.

6.1.2 Adverse Device Effects

Adverse Device Effects are any untoward or unintended responses to a medical device. This definition may include any event resulting from insufficiencies or inadequacies in the instructions for use or the deployment of the device or other device malfunctions. This definition includes any event that is a result of a user error.

6.1.3 Device Deficiency

A Device Deficiency is any inadequacy of the medical device with respect to its identity, quality, durability, reliability, safety or performance. This includes malfunctions, use errors and inadequate labeling. A malfunction is any failure of a medical device to perform in accordance with its intended purpose when used in accordance with the instructions for use or clinical study protocol. All device deficiencies are classified as product complaints and are to be reported to the Sponsor as described in Section 6.3.3.

6.2 Evaluation

Adverse events experienced in this study may be associated with the study device (i.e., ADE) or the study protocol.

When evaluating AEs, the Investigator must determine if the event is serious, assess the severity of symptoms, and evaluate the relationship of the event to the study device and study protocol, using the following guidelines:

A **Serious Adverse Event (SAE)** is any AE (ocular or non-ocular) that:

- results in death
- results in serious injury, defined as:
 - life-threatening
 - permanent impairment of a body structure or function (e.g., blindness)
 - necessitates medical or surgical intervention to prevent permanent impairment to a body structure or a body function, or
 - results in a potentially sight-threatening condition;
- is a malfunction that might cause or contribute to a serious injury or death if it were to recur
- requires in-patient hospitalization or prolongation of existing hospitalization¹
- leads to fetal distress, fetal death, a congenital abnormality, or birth defect

¹Hospitalization is a criterion for assessment of seriousness. Hospitalization in the absence of a medical AE is not in itself an AE. For example, the following reports of hospitalization without a medical AE should not be considered either serious, or an AE:

- administrative admission (e.g., for yearly monitoring exam)
- optional admission not associated with a worsening of a pre-existing condition (e.g., scheduled repair of the rotator cuff)
- hospitalization for admission without a medical AE

Severity

- Mild: Subject awareness of a sign or symptom that is easily tolerated, requires no treatment, and does not interfere with the subject's daily activities
- Moderate: Subject awareness of a sign or symptom which may be a low level of concern to the subject and may interfere with daily activities, but can be relieved by simple therapeutic care
- Severe: A sign or symptom that interrupts the subject's daily activity and requires systemic therapy or other treatment

Relationship (Causality) to Study Device or Study Protocol

- Not Related: Adverse events which are clearly and incontrovertibly due to causes other than the study device or study protocol (e.g., concomitant disease, etc.)

- **Related:** Adverse events which are felt with a reasonable degree of certainty to be related to the study device or study protocol
- **Unknown:** Adverse events for which a connection with the study device or study protocol cannot be ruled-out with certainty, or not enough information is available to assess the relationship

6.3 Reporting

6.3.1 On-Site Expedited Reporting

The Investigator is obligated to report the following to the Sponsor within 24 hours of becoming aware of the event to ensure the safety of all participants in the study and to meet regulatory reporting requirements:

- all **SAEs**, regardless of relationship to study device or study protocol,
- all secondary surgical interventions (removal, replacement or repositioning) involving the study lens and events that cause these interventions,
- loss of CDVA ≥ 10 letters compared to the baseline (Preop Visit) at Postoperative Visit 5 (Day 147-182), or later
- all **non-serious AEs** determined to be related to the study device (ADEs)
- all device malfunctions that do not result in one of the above reportable events

When reporting these events to the Sponsor, the site should forward any supporting documents along with the appropriate reporting form and the corresponding CRF, if applicable. Refer to the Personnel and Facilities section for Sponsor contact information for reporting of SAEs/ADEs and device malfunctions. Sites must also report applicable events to the reviewing IRB per its established reporting procedures.

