Inclusion criteria:	
 1. Subjects 21 through 45 years old at time of surgery. 2. For EVO/EVO+ ICL for Myopia: 
 • Moderate to high myopia ranging from -3.00 D to ≤ -20.00 D spherical equivalent (SE) in the spectacle plane, with less than or equal to 2.50 D of astigmatism (in the spectacle plane). 
For EVO/EVO+ Toric ICL for Myopia with Astigmatism:
 
 • Moderate to high myopic astigmatism with spherical equivalent ranging from -3.00 D to ≤ -20.00 D (in the spectacle plane) and cylinder in the range of 1.00 D to 4.00 D (in the spectacle plane). • Stable refractive history within 0.50 D cylinder for 1 year prior to implantation as determined by the Investigator. 3. Stable refractive history within 0.50 D for spherical equivalent 1 year prior to implantation as determined by the Investigator. 4. For a subject who is expected to have residual postoperative cylindrical refractive error of ≥ 1 D (as determined by STAAR Online Calculation and Ordering Software, OCOS), the subject should be given the opportunity to experience his/her vision with the anticipated correction. 5. Anterior chamber depth (ACD) 3.00 mm or greater, when measured from the corneal endothelium to the anterior surface of the crystalline lens. 6. Meet minimum endothelial cell density (ECD) requirements for age and ACD (refer to the “Minimum ECD for Age and True ACD*” table below).

STAAR Surgical Company Study #CP19-01	

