	
diameter central port. The lens is manufactured from Collamer, a proprietary hydroxyethyl methacrylate (HEMA)/porcine-collagen biocompatible polymer material with an ultraviolet (UV) absorber. The lens is manufactured in four overall diameters: 12.1, 12.6, 13.2, and 13.7 mm to accommodate different eye sizes and feature a plate-haptic design with a central convex/concave optical zone and incorporate a forward vault to minimize contact with the central anterior capsule. The lens is supplied with a delivery system for implantation through an incision of 3.5 mm or less.
 
EVO/EVO+ lenses have orientation markings on the footplates to ensure they are implanted in the correct orientation. When correctly oriented the orientation markings will be on the leading right/trailing left footplates.
 
The EVO/EVO+ Toric lenses are labeled using a plus cylinder axis format and have two engraved lines, one on each side of the optic to aid with the axis alignment of the lens. The following EVO/EVO+ Models will be included in this study:
 
 • EVO/EVO+ Visian Implantable Collamer Lens for Myopia: VICMO12.1, VICMO12.6, VICMO13.2, VICMO13.7, VICM5_12.1, VICM5_12.6, VICM5_13.2, VICM5_13.7 • EVO/EVO+ Visian Toric Implantable Collamer Lens for Myopia with Astigmatism: VTICMO12.1, VTICMO12.6, VTICMO13.2, VTICMO13.7, VTICM5_12.1, VTICM5_12.6, VTICM5_13.2, VTICM5_13.7 
All study lenses will be available in -3.00 D to -16.00 D spherical equivalent dioptric powers. The EVO/EVO+ Visian Toric ICLs will also be available in cylinder dioptric power of 1.00 D to 4.00 D.

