7.4 Statistical Analysis

The first primary study endpoint is defined as the incidence of PI required to treat elevated IOP caused by mechanical pupillary block through Postoperative Visit 5. The primary analysis will be performed on a minimum of 300 primary eyes that have completed Postoperative Visit 5. Based on complaint data, the SPE rate for secondary PI required to treat elevated IOP caused by mechanical pupillary block is approximately 0.3% for MICTL/TMICTL. Based on the recommended analysis in ISO 11979-7:2018, Annex E, the maximum number of cases allowed before the SPE rate is exceeded for 300 primary eyes of 300 subjects is 3.

The other primary endpoints will be studied using the first treated (i.e., primary) eyes. Secondary endpoints and additional study parameters will be studied using all (primary and fellow) eyes. Data will be summarized with point estimates and exact binomial confidence intervals for binary outcomes such as MRSE within 0.50 D and 1.00 D of target and UDVA 20/40 or better. Continuous outcomes (e.g., %hex, CV) will be described with summary statistics to include N, mean, standard deviation, minimum and maximum, first and third quartiles, and median. Distributions, such as CDVA loss, trabecular pigmentation, PAS, AC cells and flare will be summarized by number and percentage for each visit.

ECD loss over the 1050 – 1170 days of follow up will be modeled using a bi-exponential model with adjustment for correlation between paired eyes. ECD and change in ECD will be summarized at each visit. The number and percentage of eyes with ECD < 1000 and < 1500 will be summarized over time using descriptive statistics.

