APPENDIX B: INSTRUCTIONS FOR USE

STAAR Surgical EVO/EVO+ Visian® Implantable Collamer® Lens for Myopia, and EVO/EVO+ Visian® Toric Implantable Collamer® Lens for Myopia with Astigmatism Investigational Devices (EVO/EVO+ lenses)

Study CP19-01: INSTRUCTIONS FOR USE

Manufacturer:

STAAR Surgical Company
[name]
[name]
USA

[contact]
[contact]

CAUTION – Investigational Device. Limited by Federal (or United States) law to investigational use

INDICATIONS

The **EVO/EVO+ ICL for myopia** is indicated for use in patients 21-45 years of age:

1. for the correction of myopia ranging from -3.0 D to \leq -15.0 D spherical equivalent (SE) in the spectacle plane, with less than or equal to 2.5 D of astigmatism (in the spectacle plane);
2. for the reduction of myopia ranging from greater than -15.0 D to -20.0 D SE (in the spectacle plane), with less than or equal to 2.5 D of astigmatism (in the spectacle plane);
3. with an anterior chamber depth (ACD) of 3.00 mm or greater, when measured from the corneal endothelium to the anterior surface of the crystalline lens, and a stable refractive history (within 0.5 D for 1 year prior to implantation).
4. The ICL is intended for placement in the posterior chamber (ciliary sulcus) of the phakic eye.

The ICL functions as a refractive element to optically reduce moderate to high myopia.

The **EVO/EVO+ Toric ICL for myopia with astigmatism** is indicated for use in patients 21-45 years of age:

1. for the correction of myopic astigmatism with spherical equivalent ranging from -3.0 D to \leq -15.0 D (in the spectacle plane) with cylinder (spectacle plane) of 1.0 D to 4.0 D.

2. for the reduction of myopic astigmatism with spherical equivalent ranging from greater than -15.0 D to -20.0 D (in the spectacle plane) with cylinder (spectacle plane) 1.0 D to 4.0 D.
3. with an anterior chamber depth (ACD) of 3.00 mm or greater, when measured from the corneal endothelium to the anterior surface of the crystalline lens and a stable refractive history (within 0.5 D for both spherical equivalent and cylinder for 1 year prior to implantation).
4. The Toric ICL is intended for placement in the posterior chamber (ciliary sulcus) of the phakic eye.

The Toric ICL functions as a refractive element to optically reduce moderate to high myopia with astigmatism.

CONTRAINDICATIONS AND EXCLUSION CRITERIA

- Younger than 21 or older than 45 years of age.
- With true ACD < 3.00 mm*.

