APPENDIX C: METHODS OF CLINICAL EVALUATION

Any changes to the procedures described in this appendix will be provided under separate cover.

1. Manifest Refraction

The refraction should be obtained by a qualified ophthalmologist, optometrist, or trained ophthalmic technician, in 0.25 D steps, in a calibrated refraction lane. If the subject has a current pair of glasses for distance vision, they can be measured with a lensometer and these measurements used as the beginning approximate refraction. If the subject does not have glasses for distance vision, retinoscopy should be performed by an examiner proficient in this procedure. If the subject is a contact lens wearer, they should be advised to arrive for preoperative testing wearing their spectacles. If the subject is a contact lens wearer, they will need to discontinue contact lens use for at least 2 weeks (rigid contact lenses and all toric contact lenses) or 3 days (non-toric soft contact lenses) prior to the first refraction.

AUTOREFRACTION ALONE IS NOT ALLOWED AT ANY POINT IN THIS STUDY. RESULTS MUST BE REFINED USING SUBJECTIVE TECHNIQUES.

The manifest refraction (adjusted for optical infinity as necessary) will be carried out using a standard “push plus” procedure, in 0.25 D increments and utilizing Jackson Cross-cylinder to assess toricity. The end result of the refraction must ensure the manifest refraction outcome reflects the very minimum “minus” power required to read the smallest line possible. If adding -0.25 D does not result in an additional letter read, it must not be added. Further, if adding +0.25 D does not result in a loss of letters read, it must be added.

The manifest subjective refraction result, adjusted for optical infinity, **MUST** be transferred to the trial frame for CDVA testing. The power of the lens used for the distance adjustment is subtracted from the sphere power before recording the refraction. For example, for testing at 4 meters, the power of the lens used for the distance adjustment is +0.25 D. The manifest refraction spherical power is +0.25 D less than the total sphere power measured at 4 meters. Both the adjusted and unadjusted manifest refractions should be recorded, if applicable.

2. Visual Acuity Testing

a) Equipment

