Corrected (CDVA) and uncorrected visual acuity (UDVA) at all scheduled visits will be measured using the Early Treatment of Diabetic Retinopathy Study (ETDRS) charts at 4 meters or an equivalent optotype-adjusted distance (i.e., a projected or digital ETDRS chart may be placed at a distance other than 4 meters to accommodate the size of the examination room; however, the size of the optotype should be calibrated accordingly). UDVA should be performed using a trial lens with power of +1.00 D/(distance of chart in meters) to place the chart at optical infinity. CDVA (corrected distance visual acuity)

should be performed using a trial lens power reflecting the corresponding CDVA refraction.

The charts are designed according to the following principles described by Bailey and Lovie¹² and the National Academy of Science-National Research Council (NAS-NRC) Committee on Vision 1980¹³: 1) letters of equal legibility; 2) combine the letters so that each line is of approximately equal difficulty as described by Ferris et al¹⁴; 3) present five letters at each acuity level; 4) space rows by the height of the smaller letter; 5) space letters by the width of same-sized letters; and 6) use a logarithmic progression of letter size from LogMAR (Logarithm of Minimal Angle of Resolution) -0.3 (20/10) to 1.68 (20/957). This standard describes a single method for the measurement of VA (which is strongly influenced by the methods used in the ETDRS and AREDS protocols) so that measurements obtained using the procedures listed below can be compared within and between sites.¹⁴

b) Testing Methods

In order to provide standardized and well-controlled assessment of VA, all VA assessments for a subject should be performed consistently (e.g., the same lighting conditions, viewing distance, etc.) at each visit.

During acuity testing, vision testers should:

- observe subjects carefully for squinting (or head turning, etc.) and frequently remind patients not to squint or turn their heads,
- inform subjects that the chart has letters only, no numbers. If the subject reads a number, he or she should be reminded that the chart contains no numbers, and the examiner should then request a letter in lieu of the number.
- The subject should be asked to read slowly, about one letter per second, so as to achieve the best identification of each letter. He/she is not to proceed to the next letter until he/she has given a definite response.

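### CDVA loss is scored against preoperative trial-frame acuity, which minification lowers in high myopes and implantation largely restores, so the 10-letter rule misses some losses a few letters above its threshold

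*Combined protocol and SAP*

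**What the plan says.** - **Expedited rule (6.3.1).** Sites report within 24 hours a "loss of CDVA ≥ 10 letters compared to the baseline (Preop Visit) at Postoperative Visit 5" or later. This is the only CDVA-loss rule that names its reference.
- **AE rule (6.1.1).** An AE is due for "loss of CDVA ≥ 10 letters at any time point > 1 week postoperatively". No reference visit is given. AE incidence through Visit 5 is one of the primary endpoints (7.1.1).
- **Summary (7.4).** "Distributions, such as CDVA loss, trabecular pigmentation, PAS, AC cells and flare will be summarized by number and percentage for each visit". Again no reference is given. CDVA is followed through Visit 8 (7.1.3).
- **Measurement (Appendix C, items 1 and 2).** The manifest refraction must "be transferred to the trial frame for CDVA testing". The charts "present five letters at each acuity level". Neither a vertex distance nor an image-size adjustment is mentioned.
- **Refractive range (synopsis; 3.2.1.1).** "Moderate to high myopia ranging from -3.00 D to ≤ -20.00 D spherical equivalent (SE) in the spectacle plane".
- **Postoperative target (Appendix B, lens power calculation).** Emmetropia, within 0.50 D.
- **Lens power.** The synopsis says "All study lenses will be available in -3.00 D to -16.00 D spherical equivalent dioptric powers"; Table 1 stops the EVO+ models at -14.00 D. Above -15 D the indication in Appendix B is "for the reduction of myopia ranging from greater than -15.0 D to -20.0 D SE (in the spectacle plane"), as opposed to correction.

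**The concern.** A minus lens in front of the eye makes the retinal image smaller, and the effect grows with its power. Before surgery CDVA is read through a trial lens of -3 to -20 D. After surgery the trial frame holds little, where the implant's power suffices. Measured change from the preoperative visit is therefore real change plus an optical gain that rises with myopia.

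The consequence is an effective threshold above 10 letters that differs between eyes. It is highest in the higher myopes, the group for whom Appendix B itself warns of higher AE rates (Precautions) and possibly higher long-term cataract risk (Warnings). For illustration, take a -10 D eye that gains 3 letters after surgery and has lost 12 from that level by Visit 7. It shows a loss of 9 letters from the preoperative visit, and the expedited rule does not fire on acuity. The 12-letter fall is nonetheless in the trial's own data, because CDVA is scheduled at every visit from Visit 2 on (Appendix A).

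**Working it through.** **The plan's nearest figure.** The documents give no figure for minification. The related statement in 7.2 is that 300 eyes give 95% probability of seeing an AE with a true rate of 1%. It reproduces: 1 - 0.99^300 = 0.951.

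**Inputs from the documents.** Myopia of -3 to -20 D in the spectacle plane; trial-frame CDVA; five letters per line; target emmetropia; lens power to -16 D.

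**Assumptions not in the documents.** A line step of 0.1 logMAR, so 0.02 per letter; letters read scale with image size; vertex distance v of 10 to 14 mm; entrance pupil 3 mm behind the cornea, so d = v + 3 mm; corneal power K of 43 to 45 D; implant 3.4 mm behind the cornea and neutral for image size.

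**Step 1: gain formula.** Image size through a trial lens of power F is proportional to 1/(1 - d·F), with d in metres. With F_pre before surgery and F_post after:

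gain in letters = 50·log10[(1 - d·F_pre)/(1 - d·F_post)]

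**Step 2: eyes that the lens can fully correct (F_post = 0), at v = 12 mm (d = 0.015).**
- -3 D: 50·log10(1.045) = 1.0
- -10 D: 50·log10(1.15) = 3.0
- -15 D: 50·log10(1.225) = 4.4

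**Step 3: eyes beyond the power limit.** Let f(V) = n/(n/V - t), with n = 1.336 and t = 0.0034 m, carry vergence from cornea to implant. The power needed is f(K + F/(1 - vF)) - f(K). At -20 D and v = 12 mm this is -19.4 to -19.7 D. With the lens capped at -16 D, the residual in the trial frame is -2.8 to -3.0 D. The gain is then 50·log10[1.30/(1 + 0.015 × 2.8)] = 4.8, or 4.7 with a residual of -3.0 D. Full correction would have given 50·log10(1.30) = 5.7.

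**Step 4: range over vertex distance.** An image-size-adjusted loss L scores as L - gain, so it is missed when L < 10 + gain.

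| Preoperative SE | Gain, v = 10 to 14 mm | Whole-letter losses scoring below 10 |
|---|---|---|
| -3 D | 0.8 to 1.1 | 10 (11 at 14 mm) |
| -8 D | 2.1 to 2.8 | 10 to 12 |
| -10 D | 2.7 to 3.4 | 10 to 12 or 13 |
| -15 D | 3.9 to 4.9 | 10 to 13 or 14 |
| -20 D, -16 D cap | 4.0 to 5.5 | 10 to 14 (15 at 14 mm) |

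Missing a 15-letter loss needs a gain above 5 letters. At v = 14 mm (d = 0.017) that is reached at F = -(10^0.1 - 1)/0.017 = -15.2 D, so in eyes of roughly -16 D or more. At v = 12 mm the cap holds the gain below 5 even at -20 D. An EVO+ lens, limited to -14 D, leaves a larger residual and so a smaller gain in the highest myopes.

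**Step 5: what masking would do to the 7.2 statement.** If a share s of events with a true rate of 1% were masked, the probability of seeing at least one in 300 eyes is 1 - (1 - 0.01(1 - s))^300: 0.934 at s = 10%, 0.895 at 25%, 0.778 at 50%. The documents give no value for s; these are illustrations only.

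**The case against.** **Most causes of loss are captured elsewhere.** Section 6.1.1 lists corneal edema, macular edema, retinal detachment, lens opacities and endothelial cell loss as reportable. It also lists loss of CDVA among platform AEs with no letter threshold, and 6.3.1 expedites all SAEs and all device-related non-serious AEs. Lens grading, specular microscopy and fundus examination continue to Visit 8. This stands: a masked loss can be reported through its cause, or appear as a smaller loss in the 7.4 distribution. The masking is partial. But that distribution carries the same offset if taken from the preoperative visit, and the listed macular edema definition requires CDVA of 20/40 or worse, so it does not reliably back up a fall from a very good starting acuity.

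**Change from preoperative corrected acuity is a legitimate patient-level measure.** This also stands, and is why the rule should be kept and supplemented.

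**No decision depends on it.** AE incidence, CDVA and UDVA have no performance target. This stands and limits the weight of the point.

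**Stronger readings that a reader might infer.**
- *Losses of 10 to 15 letters generally go uncounted.* Fifteen letters is the extreme corner of the assumptions; at a 12 mm vertex a 15-letter loss is still counted at every refraction in range.
- *The implant removes all minification.* The -16 D limit and the reduction-only indication above -15 D contradict this for the highest myopes.
- *The AE rule is tied to the preoperative visit.* Section 6.1.1 names no reference; only 6.3.1 does.

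**Conclusion.** The point holds as a moderate measurement offset in one safety rule, and in 6.1.1 and 7.4 as well if they use the preoperative reference. Under the stated assumptions the effective threshold is about 13 letters at -10 D and 14 to 15 at -15 to -20 D (12 mm vertex), against about 11 at -3 D.

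The direction follows from where the correction sits before and after surgery. The size rests on standard optics with an assumed vertex distance and letter step, and on expected values without test-retest noise. The documents give no distribution of preoperative refraction, so the number of affected eyes cannot be estimated. The sample size and the pupillary-block endpoint are untouched. It is worth correcting because the remedy uses data already scheduled.

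**What to change.** 1. Keep the preoperative reference for the AE and expedited rules, and state it explicitly in 6.1.1 and 7.4.
2. In 7.4, add a supplementary count of eyes with CDVA loss of 10 letters or more from the eye's own early postoperative CDVA. Use one fixed visit, for example Visit 4 (Day 70 to 98), compared with Visits 5 to 8. Visit 4 falls after the perioperative medication taper ends at Day 28, whereas the Visit 3 window (Day 21 to 35) straddles it. Taking the better of two readings would select the higher of two noisy values and inflate later losses. This comparison needs no optical assumption.
3. In 7.4, tabulate CDVA change from the preoperative visit by preoperative SE band.
4. If an optically corrected change is shown, use both refractions: 50·log10[(1 - d·SE_pre)/(1 - d·SE_post)], with d stated as an assumption and its range shown. Using the preoperative value alone over-adjusts eyes with residual myopia.

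The cost is a wording clarification, one or two extra tables, and a few more eyes flagged. The Visit 4 reference does not capture loss already present at that visit; the retained preoperative rule covers such loss, but only subject to the same optical offset.
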